## 6.3 Tables and Listings

### LIST OF TABLES

| Number        | Title   | Topline |
|---------------|---|---------|
| 15.1   | Disposition and Demographics   |         |
| 15.1.1        | Eligibility of Subjects and Analysis Sets – All Subjects  |         |
| 15.1.2        | Overall Assessment: Reason for Premature Discontinuation – All Subjects   |         |
| 15.1.3.1      | Demographic Data – BFAS   | ✓       |
| 15.1.3.2      | Demographic Data – BIAS   |         |
| 15.1.4        | Medical History by System Organ Class and Preferred Term – BFAS   |         |
| 15.1.5        | Concomitant Medication During the Booster Phase by ATC Class – BFAS   |         |
| 15.1.6        | Compliance: Number of Subjects Who Completed Memory Aids – BFAS   |         |
|               |   |         |
| 15.2   | Immunogenicity   |         |
| 15.2.1 | Serum RSV-specific PRNT Strain A   |         |
| 15.2.1.1      | Serum RSV-specific PRNT Strain A: Geometric Mean Titer – BFAS   | ✓       |
| 15.2.1.2      | Serum RSV-specific PRNT Strain A: Geometric Mean Titer by Age Group – BFAS  |         |
| 15.2.1.3.1    | Serum RSV-specific PRNT Strain A: Fold Increase – BFAS  | ✓       |
| 15.2.1.3.2    | Serum RSV-specific PRNT Strain A: Fold Increase from Main Baseline - BFAS   |         |
| 15.2.1.4      | Serum RSV-specific PRNT Strain A: Fold Increase by Age Group – BFAS   |         |
| 15.2.1.5      | Serum RSV-specific PRNT Strain A: Positivity Rates – BFAS   |         |
| 15.2.1.6      | Serum RSV-specific PRNT Strain A: Response Rates – BFAS   | ✓       |
| 15.2.1.7      | Serum RSV-specific PRNT Strain A: Geometric Mean Titer Ratios Between Dose Groups – BFAS                              | ✓       |
| 15.2.1.8      | Serum RSV-specific PRNT Strain A: Geometric Mean Titer Ratios Between Booster Sub-study and Main Study – BFAS         | ✓       |
| 15.2.1.9      | Serum RSV-specific PRNT Strain A: Geometric Mean Fold Increase Ratios Between Dose Groups – BFAS                      | ✓       |
| 15.2.1.10     | Serum RSV-specific PRNT Strain A: Geometric Mean Fold Increase Ratios Between Booster Sub-study and Main Study – BFAS | ✓       |
|               |   |         |
| 15.2.2 | Serum RSV-specific PRNT Strain B   |         |
| 15.2.2.1      | Serum RSV-specific PRNT Strain B: Geometric Mean Titer – BFAS   | ✓       |
| 15.2.2.2.1    | Serum RSV-specific PRNT Strain B: Fold Increase – BFAS  | ✓       |

| Number        | Title   | Topline |
|---------------|---|---------|
| 15.2.2.2.2    | Serum RSV-specific PRNT Strain B: Fold Increase from Main Baseline – BFAS   |         |
| 15.2.2.3      | Serum RSV-specific PRNT Strain B: Positivity Rates – BFAS   |         |
| 15.2.2.4      | Serum RSV-specific PRNT Strain B: Response Rates – BFAS   | ✓       |
| 15.2.2.5      | Serum RSV-specific PRNT Strain B: Geometric Mean Titer Ratios Between Dose Groups – BFAS                              | ✓       |
| 15.2.2.6      | Serum RSV-specific PRNT Strain B: Geometric Mean Titer Ratios Between Booster Sub-study and Main Study – BFAS         | ✓       |
| 15.2.2.7      | Serum RSV-specific PRNT Strain B: Geometric Mean Fold Increase Ratios Between Dose Groups – BFAS                      | ✓       |
| 15.2.2.8      | Serum RSV-specific PRNT Strain B: Geometric Mean Fold Increase Ratios Between Booster Sub-study and Main Study – BFAS | ✓       |
|               |   |         |
| 15.2.3 | RSV-specific IgA ELISA (serum)   |         |
| 15.2.3.1      | Serum RSV-specific IgA ELISA: Geometric Mean Titer – BFAS   | ✓       |
| 15.2.3.2      | Serum RSV-specific IgA ELISA: Geometric Mean Titer by Age Group – BFAS  |         |
| 15.2.3.3.1    | Serum RSV-specific IgA ELISA: Fold Increase – BFAS  | ✓       |
| 15.2.3.3.2    | Serum RSV-specific IgA ELISA: Fold Increase from Main Baseline – BFAS   |         |
| 15.2.3.4      | Serum RSV-specific IgA ELISA: Fold Increase by Age Group – BFAS   |         |
| 15.2.3.5      | Serum RSV-specific IgA ELISA: Positivity Rates – BFAS   |         |
| 15.2.3.6      | Serum RSV-specific IgA ELISA: Response Rates – BFAS   | ✓       |
| 15.2.3.7      | Serum RSV-specific IgA ELISA: Geometric Mean Titer Ratios Between Dose Groups – BFAS                                  | ✓       |
| 15.2.3.8      | Serum RSV-specific IgA ELISA: Geometric Mean Titer Ratios Between Booster Sub-study and Main Study – BFAS             | ✓       |
| 15.2.3.9      | Serum RSV-specific IgA ELISA: Geometric Mean Fold Increase Ratios Between Dose Groups – BFAS                          | ✓       |
| 15.2.3.10     | Serum RSV-specific IgA ELISA: Geometric Mean Fold Increase Ratios Between Booster Sub-study and Main Study – BFAS     | ✓       |
|               |   |         |
| 15.2.4 | RSV-specific IgG ELISA (serum)   |         |
| 15.2.4.1      | Serum RSV-specific IgG ELISA: Geometric Mean Titer – BFAS   | ✓       |
| 15.2.4.2.1    | Serum RSV-specific IgG ELISA: Fold Increase – BFAS  | ✓       |
| 15.2.4.2.2    | Serum RSV-specific IgG ELISA: Fold Increase from Main Baseline – BFAS   |         |
| 15.2.4.3      | Serum RSV-specific IgG ELISA: Positivity Rates – BFAS   |         |
| 15.2.4.4      | Serum RSV-specific IgG ELISA: Response Rates – BFAS   | ✓       |
| 15.2.4.5      | Serum RSV-specific IgG ELISA: Geometric Mean Titer Ratios Between Dose Groups – BFAS                                  | ✓       |

| Number        | Title  | Topline |
|---------------|--|---------|
| 15.2.4.6      | Serum RSV-specific IgG ELISA: Geometric Mean Titer Ratios Between Booster Sub-study and Main Study – BFAS                            | ✓       |
| 15.2.4.7      | Serum RSV-specific IgG ELISA: Geometric Mean Fold Increase Ratios Between Dose Groups – BFAS   | ✓       |
| 15.2.4.8      | Serum RSV-specific IgG ELISA: Geometric Mean Fold Increase Ratios Between Booster Sub-study and Main Study – BFAS                    | ✓       |
|               |  |         |
| 15.2.5 | RSV-strain A G protein-specific IgG ELISA (serum)   |         |
| 15.2.5.1      | Serum RSV-strain A G protein-specific IgG ELISA: Geometric Mean Titer – BFAS   | ✓       |
| 15.2.5.2.1    | Serum RSV-strain A G protein-specific IgG ELISA: Fold Increase – BFAS  | ✓       |
| 15.2.5.2.2    | Serum RSV-strain A G protein-specific IgG ELISA: Fold Increase from Main Baseline – BFAS   |         |
| 15.2.5.3      | Serum RSV-strain A G protein-specific IgG ELISA: Positivity Rates – BFAS   |         |
| 15.2.5.4      | Serum RSV-strain A G protein-specific IgG ELISA: Response Rates – BFAS   | ✓       |
| 15.2.5.5      | Serum RSV-strain A G protein-specific IgG ELISA: Geometric Mean Titer Ratios Between Dose Groups – BFAS                              | ✓       |
| 15.2.5.6      | Serum RSV-strain A G protein-specific IgG ELISA: Geometric Mean Titer Ratios Between Booster Sub-study and Main Study – BFAS         | ✓       |
| 15.2.1.5.7    | Serum RSV Strain A G protein-specific IgG ELISA: Geometric Mean Fold Increase Ratios Between Dose Groups – BFAS                      | ✓       |
| 15.2.1.5.8    | Serum RSV Strain A G protein-specific IgG ELISA: Geometric Mean Fold Increase Ratios Between Booster Sub-study and Main Study – BFAS | ✓       |
|               |  |         |
| 15.2.6 | RSV-strain B G protein specific IgG ELISA (serum)   |         |
| 15.2.6.1      | Serum RSV-strain B G protein-specific IgG ELISA: Geometric Mean Titer – BFAS   | ✓       |
| 15.2.6.2.1    | Serum RSV-strain B G protein-specific IgG ELISA: Fold Increase – BFAS  | ✓       |
| 15.2.6.2.2    | Serum RSV-strain B G protein-specific IgG ELISA: Fold Increase from Main Baseline – BFAS   |         |
| 15.2.6.3      | Serum RSV-strain B G protein-specific IgG ELISA: Positivity Rates – BFAS   |         |
| 15.2.6.4      | Serum RSV-strain B G protein-specific IgG ELISA: Response Rates – BFAS   | ✓       |
| 15.2.6.5      | Serum RSV-strain B G protein-specific IgG ELISA: Geometric Mean Titer Ratios Between Dose Groups – BFAS                              | ✓       |
| 15.2.6.6      | Serum RSV-strain B G protein-specific IgG ELISA: Geometric Mean Titer Ratios Between Booster Sub-study and Main Study – BFAS         | ✓       |

| Number        | Title  | Topline |
|---------------|--|---------|
| 15.2.1.6.7    | Serum RSV Strain B G protein-specific IgG ELISA: Geometric Mean Fold Increase Ratios Between Dose Groups – BFAS                      | ✓       |
| 15.2.1.6.8    | Serum RSV Strain B G protein-specific IgG ELISA: Geometric Mean Fold Increase Ratios Between Booster Sub-study and Main Study – BFAS | ✓       |
|               |  |         |
| 15.2.7 | RSV-specific IgA ELISA (mucosal)  |         |
| 15.2.7.1      | Mucosal RSV-specific IgA ELISA: Geometric Mean Titer – BFAS  | ✓       |
| 15.2.7.2.1    | Mucosal RSV-specific IgA ELISA: Fold Increase – BFAS   | ✓       |
| 15.2.7.2.2    | Mucosal RSV-specific IgA ELISA: Fold Increase from Main Baseline – BFAS  |         |
| 15.2.7.3      | Mucosal RSV-specific IgA ELISA: Positivity Rates – BFAS  |         |
| 15.2.7.4      | Mucosal RSV-specific IgA ELISA: Response Rates – BFAS  | ✓       |
| 15.2.7.5      | Mucosal RSV-specific IgA ELISA: Response Rates by Booster Baseline Titer Median – BFAS   | ✓       |
| 15.2.7.6      | Mucosal RSV-specific IgA ELISA: Geometric Mean Titer Ratios Between Dose Groups – BFAS   | ✓       |
| 15.2.7.7      | Mucosal RSV-specific IgA ELISA: Geometric Mean Titer Ratios Between Booster Sub-study and Main Study – BFAS                          | ✓       |
| 15.2.7.8      | Mucosal RSV-specific IgA ELISA: Geometric Mean Fold Increase Ratios Between Dose Groups – BFAS                                       | ✓       |
| 15.2.7.9      | Mucosal RSV-specific IgA ELISA: Geometric Mean Fold Increase Ratios Between Booster Sub-study and Main Study – BFAS                  | ✓       |
|               |  |         |
| 15.2.8 | PBMC RSV-specific IFN-<math>\gamma</math> ELISPOT Peptide Pools   |         |
| 15.2.8.1      | PBMC RSV-specific IFN- $\gamma$ (ELISPOT Peptide Pools/RSV): Positivity rates – BIAS   |         |
| 15.2.8.2      | PBMC RSV-specific IFN- $\gamma$ (ELISPOT Peptide Pools/RSV): Response rates – BIAS   | ✓       |
| 15.2.8.3      | PBMC RSV-specific IFN- $\gamma$ (ELISPOT Peptide Pools/RSV): Median and Geometric Mean SFU – BIAS                                    | ✓       |
| 15.2.8.4      | PBMC RSV-specific IFN- $\gamma$ (ELISPOT Peptide Pools/RSV): Responder Rates – BIAS  | ✓       |
| 15.2.8.5      | PBMC RSV-specific IFN- $\gamma$ (ELISPOT Peptide Pools/RSV): Responders to 1, 2, 3, 4 or 5 Peptide Pools – BIAS                      | ✓       |
|               |  |         |
| 15.2.9 | PBMC RSV-specific IL-4 ELISPOT Peptide Pools  |         |
| 15.2.9.1      | PBMC RSV-specific IL-4 (ELISPOT Peptide Pools/RSV): Positivity rates – BIAS  |         |
| 15.2.9.2      | PBMC RSV-specific IL-4 (ELISPOT Peptide Pools/RSV): Response rates – BIAS  |         |
| 15.2.9.3      | PBMC RSV-specific IL-4 (ELISPOT Peptide Pools/RSV): Median and Geometric Mean SFU – BIAS   | ✓       |

| Number          | Title   | Topline |
|-----------------|---|---------|
| 15.2.9.4        | PBMC RSV-specific IL-4 (ELISPOT Peptide Pools/RSV): Responder Rates – BIAS  |         |
| 15.3     | 14.3 Safety  |         |
| 15.3.1   | 14.3.1 Adverse Events  |         |
| 15.3.1.1        | Overview of Solicited and Unsolicited Adverse Events During the Booster Sub-study Active Trial Phase – BFAS   | ✓       |
| 15.3.1.2 | Solicited Local Adverse Events   |         |
| 15.3.1.2.1      | Solicited Local Adverse Events During the Booster Sub-study Active Trial Phase: Incidence by Maximum Intensity – BFAS   |         |
| 15.3.1.2.2      | Solicited Local Adverse Events During the Booster Sub-study Active Trial Phase: Any Grade, Grade $\geq 2$ and Grade $\geq 3$ TEAEs – BFAS                                       |         |
| 15.3.1.2.3      | Solicited Local Adverse Events During the Booster Sub-study Active Trial Phase: Summary of Duration – BFAS  |         |
| 15.3.1.2.4      | Solicited Local Adverse Events During the Booster Sub-study Active Trial Phase: Summary of Relative Day of Onset – BFAS   |         |
| 15.3.1.3 | Solicited General Adverse Events   |         |
| 15.3.1.3.1      | Solicited General Adverse Events During the Booster Sub-study Active Trial Phase: Incidence by Maximum Intensity – BFAS   |         |
| 15.3.1.3.2      | Solicited General Adverse Event Related to Vaccination during the Booster Sub-study Active Trial Phase: Incidence by Maximum Intensity – BFAS                                   |         |
| 15.3.1.3.3      | Solicited General Adverse Events During the Booster Sub-study Active Trial Phase: Summary of Duration – BFAS  |         |
| 15.3.1.3.4      | Solicited General Adverse Events During the Booster Sub-study Active Trial Phase: Summary of Relative Day of Onset – BFAS   |         |
| 15.3.1.4 | Unsolicited Adverse Events   |         |
| 15.3.1.4.1      | Treatment-Emergent Unsolicited Adverse Events During the Booster Sub-study Active Trial Phase: Incidence by System Organ Class and Preferred Term – BFAS                        | ✓       |
| 15.3.1.4.2      | Related Treatment-Emergent Unsolicited Adverse Events During the Booster Sub-study Active Trial Phase: Incidence by System Organ Class and Preferred Term – BFAS                |         |
| 15.3.1.4.3      | Grade $\geq 3$ Treatment-Emergent Unsolicited Adverse Events During the Booster Sub-study Active Trial Phase: Incidence by System Organ Class and Preferred Term – BFAS         |         |
| 15.3.1.4.4      | Related Grade $\geq 3$ Treatment-Emergent Unsolicited Adverse Events During the Booster Sub-study Active Trial Phase: Incidence by System Organ Class and Preferred Term – BFAS |         |

| Number        | Title   | Topline |
|---------------|---|---------|
| 15.3.1.4.5    | Treatment-Emergent Unsolicited Adverse Events During the Booster Sub-study Active Trial Phase: Summary of Intensity and Relationship to Trial Medication – BFAS |         |
| 15.3.2 | Serious Adverse Events   |         |
| 15.3.2.1      | Serious Adverse Events During the Booster Sub-study Active Trial Phase: Incidence by System Organ Class and Preferred Term – BFAS                               |         |
| 15.3.2.2      | Related Serious Adverse Events During the Booster Sub-study Active Trial Phase: Incidence by System Organ Class and Preferred Term – BFAS                       |         |
| 15.3.3 | Laboratory, Vital Signs, and ECG Safety Data   |         |
| 15.3.3.1      | Laboratory Data (Mean Values): Hematology – BFAS  |         |
| 15.3.3.2      | Laboratory Data (Mean Values): Biochemistry – BFAS  |         |
| 15.3.3.3      | Laboratory Abnormalities: Hematology – BFAS   |         |
| 15.3.3.4      | Laboratory Abnormalities: Biochemistry – BFAS   |         |
| 15.3.3.5      | Laboratory Data (Shift Table): Hematology – BFAS  |         |
| 15.3.3.6      | Laboratory Data (Shift Tables): Biochemistry – BFAS   |         |
| 15.3.3.7      | Vital Signs – BFAS  |         |

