## Definitions

Active trial phase	The trial phase starting with and including (Booster) Visit 1 and ending with and including (B)EAP (End of active trial phase) (V3/BV1 + 28-35 days; for details see Section 1.6 and Section 1.7 ).
Booster Baseline	Immune responses measured at BV0
Booster Substudy	Administration of a single (booster) dose of MVA-BN-RSV vaccine approximately one year after the first MVA-BN-RSV vaccination in subjects previously vaccinated with MVA-BN-RSV in the main trial.
Dose 1	Represents the nominal titer of $1 \times 10^8$ Infectious Unit (Inf.U) per 0.5 mL.
Dose 2	Represents the nominal titer of $5 \times 10^8$ Inf.U per 0.5 mL.
End of active trial phase ([B]EAP)	The last visit of the active trial phase (for details see Section 1.6 and Section 1.7 ).
Fold increase	The fold increase is defined as a subject's post-baseline titer at Visit X, divided by the baseline titer
Main Trial	In the main trial subjects receive two administrations 4 weeks apart consisting of MVA-BN-RSV Dose 1 ( $1 \times 10^8$ Inf.U), MVA-BN-RSV Dose 2 ( $5 \times 10^8$ Inf.U) or Placebo (TBS).
Nominal titer	The MVA-BN-RSV (Respiratory Syncytial Virus) vaccine is formulated at a nominal titer of $5 \times 10^8$ Inf.U per dose (0.5 mL). The actual titer will be evaluated by stability data.
Staggering visit (VS)	A visit only required by subjects enrolled into the sentinel and safety cohort in the main trial.
Subgroup	The subgroup consists of 20 subjects per treatment group in the main trial who have peripheral blood mononuclear cells (PBMC) collection as well as an additional serum and nasal swab sample collection time point one week post each vaccination. Out of this subgroup, approximately 13 subjects per treatment group will be recruited into the booster substudy.
Treatment group	Subjects are recruited into one of five treatment groups receiving different investigational medicinal product (IMP) doses and schedules.
Vaccination	Intramuscular administration of active MVA-BN-RSV vaccine or Tris-buffered saline (TBS)

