### FU2 Visit (V3 + 182-210 days)

#### The following tasks will be performed:

- Recording of new SAEs, new RSV-specific symptoms and changes to AEs/SAEs ongoing at the FU1 Visit
- Targeted physical examination including auscultation of the heart and lungs
- Evaluation of vital signs
- Recording of concomitant medication
- Blood draw for serum collection (9 mL)
- Nasal swab collection for mucosal immune response (swabs are taken from both nostrils)
- **Only for the subgroup: PBMC collection (64 mL)**

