### Booster Baseline

If not otherwise specified, “booster baseline” refers to the last measurement prior to the booster vaccination, which is performed on booster visit (BV) 1 (approximately 12 months from the first vaccination in the main study). In case of missing vital event data at the first treatment visit, the booster screening vital event data may be used to impute baseline values. These data will be summarized as baseline data without specifying the visit from which the data were derived. However, in cases where no pre-treatment values exist for a baseline parameter, the subject will be considered as having no baseline, and post-baseline changes will not be able to be calculated and will be excluded from analyses.

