## Response

For each immunogenicity assay, a response to the vaccine (applicable only for post baseline visits) is defined as either the appearance of a positive result for subjects with a negative result at baseline, or an increase by a factor of at least 2 compared to baseline for subjects with a positive result at baseline. Response status is applicable only for post baseline visits and is not calculated for subjects with missing baseline titer. Main study response is defined based on the main baseline. Booster sub-study response is defined based on the booster baseline. Post baseline visits include Visit (V) 1b, V2, V3, V3b, V4, end of active phase (EAP) visit, follow-up visit (FU) 1, and FU2 from the main study; BV1b, BV2, BEAP visit, BFU1, BFU2 and BFU3 from the booster sub-study.

The response rate at each post baseline visit is the percentage of subjects who have a positive response status out of the number of subjects with a non-missing response status at that visit.

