## 6 Appendix

### 6.1 Detection Limits (DL)

| Test  | Detection Limit (DL)       | Negative values reported                              |
|---|----------------------------|---|
| PBMC RSV-specific IFN- $\gamma$ ELISPOT (pool F, G(A), G(B), N, M2 or RSV virus)
PBMC RSV-specific IL-4 ELISPOT (pool F, G(A), G(B), N, M2 or RSV virus) | 50                         | 25 (half of the DL)                                   |
| Serum RSV-specific PRNT Strain A  | 20                         | 10 (half of the DL)                                   |
| Serum RSV-specific PRNT Strain B  |                            |   |
| Serum RSV-specific IgG ELISA  | 63                         | 31.5 (half of the DL)                                 |
| Serum RSV-specific IgA ELISA  | 100                        | 50 (half of the DL)                                   |
| Mucosal RSV-specific IgA ELISA (nasal swabs)  | 2                          | 1 (half of the DL)                                    |
| Serum RSV (strain A) G protein - specific IgG ELISA
Serum RSV (strain B) G protein- specific IgG ELISA   | no detection limit applies | negative reported as 50                               |
| RSV-specific B cell Fluorospot
IgG and IgA  | no detection limit applies | a measured percentage is considered a positive result |

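### Topline Table 15.2.7.5 sorts subjects by the same BV1 mucosal IgA reading that is the denominator of response, so the low-baseline half tends to look more responsive even if the booster does nothing

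*SAP*

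**What the plan says.** The table list in booster sub-study SAP section 6.3 contains Table 15.2.7.5, "Mucosal RSV-specific IgA ELISA: Response Rates by Booster Baseline Titer Median", produced on the BFAS and ticked for topline.

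The same SAP's General Definitions say that booster baseline "refers to the last measurement prior to the booster vaccination, which is performed on booster visit (BV) 1". The Protocol's Definitions describe it differently, as "Immune responses measured at BV0". However, the booster schedule (Protocol section 1.7, repeated in SAP section 6.2) has a nasal swab at BV1 and none at BV0, so BV1 is the only reading that can serve for mucosal IgA.

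On response, the SAP states: "Booster sub-study response is defined based on the booster baseline". A baseline-positive subject responds with "an increase by a factor of at least 2 compared to baseline for subjects with a positive result at baseline"; a baseline-negative subject responds through "the appearance of a positive result for subjects with a negative result at baseline". Section 4.5.7 repeats that booster-visit response rates use the booster baseline. Section 6.1 gives the mucosal assay a detection limit of 2, with negatives reported as 1.

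Only Groups 1 and 3 enter the sub-study, all are boosted, and nobody is randomized (SAP sections 2.1 and 2.2.1). The text of section 4.5.7 does not mention the median split. It gives no purpose for it, no rule for a pooled or per-group median, no rule for ties and no guidance on interpretation.

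**The concern.** One noisy reading does two jobs: it assigns the subject to a half, and it sets the level that the later titer must double. Measurement or day-to-day error in BV1 feeds both. Subjects whose BV1 happened to be low are over-represented in the low half, and their next reading tends to rise back towards their usual level. Subjects whose BV1 happened to be high tend to fall back.

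The natural message of such a table is that the booster works best in people with low mucosal IgA. The table will lean that way whatever the vaccine does, and all subjects in it are boosted, so it offers nothing to subtract. Differences in boostability are a stated secondary objective (booster SAP section 2.3.2), so readers will look for this pattern.

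**Working it through.** **Inputs.** The plan states no figure for this table. Response threshold: log10(2) = 0.301. The only variability in the booster SAP is for PRNT strain A, in section 4.1: SD 0.335 and SD of paired differences 0.168 (log10). Nothing is given for mucosal IgA, so SD 0.3 to 0.5 and visit-to-visit correlation 0.5 to 0.8 are assumptions.

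**Check of the section 4.1 figures.** 10^0.213 = 1.63, as stated. With 40 per group, difference 0.213 and SD 0.335, power is 80.2% (noncentral t) against 80% stated. The paired test with n = 40, 0.08 and SD 0.168 gives 83.6%, consistent with the stated value above 80%. 40/0.95 = 42.1, rounded up to 43. The inputs are read correctly.

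**Model with no booster effect.** Let B be log10 BV1 and Y the post-booster value, with equal means, SD s and correlation r, and D = Y − B.
- SD(D) = s√(2(1 − r))
- corr(D, B) = −√((1 − r)/2), negative whenever r < 1
- Rate in the low half = 2 × P(D ≥ 0.301 and B below its median); likewise above the median. Both come from the bivariate normal distribution.

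**PRNT A figures.** r = 1 − 0.168²/(2 × 0.335²) = 1 − 0.0282/0.2245 = 0.874. Overall response: 0.301/0.168 = 1.79, upper tail 3.7%. corr(D, B) = −0.251. Split: 5.2% below the median, 2.1% above.

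**Assumed range.**

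| SD | r | below median | above median |
|---|---|---|---|
| 0.3 | 0.8 | 8% | 3% |
| 0.4 | 0.7 | 24% | 9% |
| 0.5 | 0.5 | 41% | 14% |

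**Detection limit.** These results come from simulation with limit 2, negatives set to 1, SD 0.335 and within-subject SD 0.168/√2 = 0.119. The no-effect split is 13.3% v 2.1% at geometric mean 4, and 16.2% v 2.1% at geometric mean 2. Only when almost all baselines are negative does the gap become small or reverse: 4.9% v 5.5% with about 89% negative (SD 0.5, within-subject SD 0.2).

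**Same true effect in everyone.** With a uniform 1.5-fold rise and the PRNT A figures, the halves show 28.9% v 16.8%. That is a gap of 12.1 points, against 5.2 − 2.1 = 3.1 points with no effect, although the booster works equally in both halves.

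**Splitting at FU2 instead.** With FU2 value F, corr(D, F) = (r_FY − r_FB)/√(2(1 − r)). This is zero only if FU2 correlates equally with BV1 and with the post-booster visit. At SD 0.4 and r = 0.7:
- equal correlations: 16.6% v 16.6%
- 0.7 with BV1 and 0.6 with BV2: (0.6 − 0.7)/√0.6 = −0.129, giving 19% v 14%
- serial decay, 0.7 and 0.49: 22% v 11%

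**The case against.** The analysis is secondary and descriptive (booster SAP section 4.5.7), rates are given by treatment group with Clopper-Pearson intervals, and no comparison of the halves is planned. That stands. A reader might infer that the plan will declare a false difference about half the time, because a z-test pooling 86 subjects at SD 0.4 and r = 0.7 rejects in 50% of simulated null trials. The documents do not support that reading. No such test is specified; within one group of 43 the z-test would reject in 25%, and the per-group intervals would fail to overlap in only 2%. With the PRNT A figures the pooled test rejects in 9%.

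The size is also uncertain. If mucosal IgA were as stable as serum PRNT A, the no-effect gap would be about 3 points. Swab titers may be noisier, but the documents do not say so.

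A reader might further infer that splitting at FU2 cures the problem. FU2 swabs are scheduled for all subjects ("Nasal swab collection for mucosal immune response (swabs are taken from both nostrils"), but FU2 falls 182 to 210 days after V3, while BV1 comes about 11 to 13 months after first vaccination. Equal correlation with BV1 and BV2 is therefore doubtful, and the table would then describe an earlier titer instead of the level at boosting.

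Two limits of scope also stand. The table shells are in a separate document, so visits and footnotes cannot be checked. If main-study visits are shown, their responses use the main baseline and the shared-denominator argument does not reach them. None of this removes the direction of the artefact at booster visits.

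**Conclusion.** The point holds for booster visits. The direction follows from the SAP's own definitions and needs only some within-subject or assay variation; it fails only if nearly all baselines are below the limit of 2. The size cannot be fixed from the documents: about 5% v 2% if mucosal IgA behaves like PRNT A, and 8% v 3% to 41% v 14% over the assumed range. Those figures assume normal log10 titers with equal variance at the two visits and, apart from the stated checks, no detection limit.

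This is a risk of misreading one topline table. It does not affect the primary result or the unsplit response, GMT and fold-increase tables, and it does not show that the booster has no effect. A cheap reference and a footnote are worth adding.

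**What to change.** Keep Table 15.2.7.5 and make two additions in the booster SAP:

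1. Print beside it the same split for main-trial placebo Group 5: halves at the V1 median, response at V2 against V1. Both swabs are scheduled for all subjects, the main SAP defines response in the same way, and V2 follows V1 by 12 to 16 days, as BV2 follows BV1. State the median and tie rule and use the same rule in both panels.
2. Add a footnote that a gap between halves no larger than the Group 5 gap is not evidence of a better booster effect at low baseline. It should be read one way only: a uniform true effect can widen the gap, as shown above, so a larger gap is not proof either.

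A split at the FU2 median may be added as a sensitivity table, labelled as using an earlier titer and as reducing, not necessarily removing, the artefact. Subjects without an FU2 swab drop out of it.

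The cost is one extra run on existing data and a few lines of SAP text. Group 5 is an approximate reference: its swabs come from a different calendar time and its subjects were never primed.
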